Long-term outcomes of successful chronic total occlusion percutaneous coronary interventions using the antegrade and retrograde dissection and re-entry approach.

(LOTUS-ADR/RDR)

Protocol

Sponsored by: Department of Cardiology, Xi'jing Hospital.

The Fourth Military Medical University (FMMU)

Approved by: Ethics Committee, Xi'jing Hospital. FMMU

Approved Ethical Number: KY20172019-1

Approved date: 2017.03.15

Last Update: 2018.11.20

Study Time: 2018.12.01- 2019.12.30

Versions: V2.0

ABSTRACT

BACKGROUND: Chronic total occlusion (CTO) angioplasty is one of the most challenging procedures remaining for the interventional operator. Today, with contemporary CTO negotiation available strategies and significant operator expertise, the literature reports a 50-95% success rate for recanalizing CTOs. But PCIs of CTO lesions still carry a high rate of in-stent restenosis (ISR). Because previous reports have not specifically compare contemporary antegrade and retrograde dissection and re-entry dissection (ADR/RDR) technique on the long-term impact of ISR, so the investigators focused on the objective.

OBJECTIVES: This study hope to evaluate the frequency of angiographic ISR and further elucidate some ISR related higher risk factors among CTO PCI patients in intimal stent group using antegrade or retrograde wire escalation (AWE/RWE) techniques and sub-intimal stent group using contemporary antegrade or retrograde dissection and re-entry (ADR and/or RDR).

METHODS: A total of 300 consecutive selected patients with CTO lesion who will undergo successful revascularization by AWE/RWE and ADR/RDR techniques treatment will be enrolled in this prospective multicenter registry from December 1 2018 to December 31 2019. The primary study endpoint of the protocol is the binary in-stent restenosis of CTO vessels at angiographic follow-up about 13 months. The secondary endpoints are: 1) CTO technique and procedure success rate; and 2) in-hospital and 30 days MACE (Cardiac death, acute myocardial infarction, urgent repeat target vessel revascularization with either pericardiocentesis or surgery and stroke and stent thrombosis and stroke); 6months and 1-year and 2-year MACE including death, MI, and target CTO vessel revascularization and stroke ; and 3) Restenosis scores (R-scores) of related risk factors.

CONCLUSIONS: This study expect to identify long-term effect of ADR and RDR methods on the ISR incidence and predictors.

INTRODUCTION

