④ Patients will sign written informed consent for long-term telephone FU before the interventional procedure. The patients will be followed by a clinical visit or by a telephone interview for 30 day, 6 months and 12 months and 24 months post-procedure for assessment of adverse events. All patients with successful CTO PCI and without moderate or severe renal insufficiency will be scheduled for angiographic follow-up at 13 months. Compared with CTA, coronary angiography to evaluate restenosis is appropriate in all patients especially for severe coronary heart diseases patients with atrial fibrillation and ventricular arrhythmia. It could provide accurate information about mild-severe angulation lesion and the stent straits like total stent length. Procedural and outcome data collection will be collected and entered by operators entered into a dedicated database.

⑤ The study will be performed in accordance with the Declaration of FMMU.

2. Study endpoints and definitions

① The primary study endpoint of the protocol is the binary in-stent restenosis of CTO vessels at the scheduled angiographic follow-up at 13 months. The secondary endpoints are: 1) CTO technique and procedure success rate; and 2) in-hospital and 30 days MACE (Cardiac death, acute myocardial infarction, urgent repeat target vessel revascularization with either pericardiocentesis or surgery and stroke and stent thrombosis and stroke); 6 months and 1-year and 2-year MACE including death, MI, and target CTO vessel revascularization and stroke ; and 3) Restenosis scores (R-scores) of related risk factors.

② Coronary CTOs will be defined as angiographic evidence of total occlusions with TIMI (Thrombolysis In Myocardial Infarction) flow grade 0 and estimated durations of at least 3 months. Estimation of the occlusion duration is based on first onset of anginal symptoms, prior history of myocardial infarction in the target vessel territory, or comparison with a prior angiogram.

③ Procedural success will be defined as angiographic success (final residual stenosis $<30\%$ by visual estimation and TIMI flow grade 3 after CTO recanalization).

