⑦ All deaths are considered cardiac unless otherwise documented. Stent thrombosis is defined according to the Academic Research Consortium criteria (13). Reocclusion is defined as a TIMI flow grade of 0 to 1 in the target CTO vessel, where restenosis is defined as > 50% luminal narrowing at the segment site, including the stent and 5 mm proximal and distal to the stent edges. Target lesion revascularization (TLR) is defined as any repeat PCI or coronary artery bypass graft surgery of the target lesion that includes 5 mm proximal and distal to the stented vessel segment.

⑧ A procedure is considered retrograde if an attempt is made to cross the lesion through a collateral vessel supplying the target vessel distal to the lesion. Complex lesions with unclear location of the proximal cap or with poor distal target are initially attempted by the retrograde approach. In those cases, after positioning of a microcatheter at the distal CTO cap, a true-to-true retrograde lumen crossing technique is first attempted for shorter lesions (<20 mm). When entering in the subintimal space or with longer lesions, knuckled wires are used to reach the proximal cap, followed most often by reverse-controlled anterograde and retrograde re-entry techniques.

⑨ A procedure is considered antegrade if no retrograde crossing attempts are made. An antegrade approach is initially attempted for short lesions (<20 mm) with clear proximal cap location and good distal vessel target using a wiring strategy. Anterograde dissection/re-entry using dedicated devices (CrossBoss and Stingray catheters) is, however, preferred for longer lesions with an optimal distal re-entry zone, without significant side branches that could be occluded by the technique, or when an initial wire escalation strategy failed. Wire-based anterograde dissection/re-entry was also used successfully when an initial attempt at crossing from a “true-to-true” approach failed. Such a strategy involves the use of a microcatheter delivered on a knuckled polymer-jacketed wire advanced into the subintimal dissection plane, with subsequent re-entry into the true distal lumen using a stiff tapered guidewire or a knuckled guidewire. A Stingray system will be used to cross from the false lumen to the true lumen, the so-called hybrid procedure, rapidly switching from one approach to another when the initial strategy attempted is failing.

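### The primary endpoint is read only at the scheduled 13-month angiogram, so restenosis re-treated earlier can count as a non-event; its in-stent label also conflicts with the in-segment definition

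*Combined protocol and SAP*

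**What the plan says.** METHODS section 2, item 1 defines the primary endpoint as "binary in-stent restenosis of CTO vessels at the scheduled angiographic follow-up at 13 months". The Abstract has "binary in-stent restenosis of CTO vessels at angiographic follow-up about 13 months". Neither gives a visit window. METHODS section 1, item 4 says who has the film: "All patients with successful CTO PCI and without moderate or severe renal insufficiency will be scheduled for angiographic follow-up at 13 months".

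Re-treatment is captured elsewhere. The secondary endpoints include "6 months and 1-year and 2-year MACE including death, MI, and target CTO vessel revascularization and stroke", and the Cox model in METHODS section 4 has target CTO vessel revascularization among its outcomes. Both work at vessel level. Target lesion revascularization is defined in section 2, item 7, for a "target lesion that includes 5 mm proximal and distal to the stented vessel segment", but no endpoint or model uses it.

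On the zone, item 7 gives the only definition: "restenosis is defined as > 50% luminal narrowing at the segment site, including the stent and 5 mm proximal and distal". The same item adds "Reocclusion is defined as a TIMI flow grade of 0 to 1 in the target CTO vessel". The logistic regression in section 4 takes re-occlusion and in-segment restenosis as its outcome. The endpoint name, in both the Abstract and section 2, is in-stent.

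**The concern.** The endpoint is status at one late film. Suppose restenosis is found and re-treated at month 7 and the lesion is open at month 13. Read as written, that patient is a non-event. If the repeat procedure leads the site to skip the scheduled film, the patient has no value at all. No section corrects either outcome, and none says how an unscheduled angiogram counts. The adverse-event contacts at 30 days, 6 months and 12 months, and the revascularization component of MACE, show that the plan expects such patients.

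At stake is the main result. The reported restenosis rate falls short of the proportion who had restenosis by 13 months. The subintimal versus intimal comparison can shift in either direction if early re-treatment differs by technique.

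The label conflict is smaller. A narrowing confined to the 5 mm beyond a stent edge is an event under the item 7 definition and in the logistic model, but not under the endpoint's name.

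**Working it through.** **The plan's own figure.** METHODS section 1, item 2 wants 60 ADR/RDR patients at a share of 20-25%. 60/0.20 = 300, which is the stated total; 60/0.25 = 240. The illustration uses 60 subintimal and 300 - 60 = 240 intimal patients, which supposes that all are successfully treated and eligible for the film. The rates and odds ratios below do not depend on these numbers. The plan states no restenosis rate, effect size or power, so there is nothing else to reproduce.

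**Assumptions (none is in the documents).** True restenosis by 13 months is p = 0.15 in both groups. A share c of these lesions is re-treated before the scheduled film.

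**Reported rate.**
- Re-treated lesions all open at month 13 and scored so: p(1 - c). For c = 0.2, 0.15 × 0.8 = 12.0%. For c = 0.3, 0.15 × 0.7 = 10.5%.
- Re-treated patients have no value: p(1 - c)/(1 - pc). For c = 0.2, 0.120/0.970 = 12.4%. For c = 0.3, 0.105/0.955 = 11.0%.

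**Group comparison, true odds ratio 1.** For shares of 30% and 20%, scored open: (0.105/0.895)/(0.120/0.880) = 0.1173/0.1364 = 0.86. With the groups exchanged it is 1.16. If a fraction of the re-treated lesions, say 30%, has narrowed again by month 13, the reported rate is p(1 - 0.7c).

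| Shares re-treated early | All open at month 13 | 30% narrowed again | No value |
|---|---|---|---|
| 30% and 20% | 0.86 or 1.16 | 0.91 or 1.10 | 0.88 or 1.14 |
| 40% and 20% | 0.73 or 1.38 | 0.82 or 1.22 | 0.75 or 1.33 |

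The first figure applies when the subintimal group has the larger share, the second when the intimal group has.

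**Test size.** For a two-sided 5% Pearson chi-square test without continuity correction (60 vs 240, both binomials enumerated), rejection is 4.8% with no loss. With shares of 30% and 20%, all open, it is 4.9% or 7.0%.

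**A true difference.** If restenosis is truly 20% vs 10% and 25% is re-treated early in both groups, the film shows 0.20 × 0.75 = 15.0% vs 0.10 × 0.75 = 7.5%. The difference shrinks from 10 to 7.5 points even with equal shares.

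**A trap in the repair.** Suppose early events are counted but event-free patients without a film are dropped. With p = 0.15, c = 0.3 and attendance a unrelated to outcome, the rate is (0.045 + 0.105a)/(0.045 + 0.955a). This gives 17.5%, 16.3% and 15.4% at a = 0.60, 0.75 and 0.90, against a true 15%.

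**The case against.** The strongest reply is that a point-in-time reading may be what the investigators want. The aim to "identify long-term effect of ADR and RDR methods on the ISR incidence and predictors" comes from the Abstract's conclusions and suggests a cumulative count. But the Abstract's objectives and METHODS section 1 speak of the frequency of angiographic restenosis, which fits status at one film. This stands in part: the film-only result understates restenosis only if the target is restenosis by 13 months. Even for a point-in-time target, however, scoring a repaired lesion as never having failed does not describe how the index stenting fared.

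Second, every rate above is assumed, and the larger shifts need sizeable differences in re-treatment between groups. That stands. In a group of 60, 15% is 9 restenoses, so shares of 30% and 20% are 2.7 and 1.8 patients.

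Third, the trial is described as exploratory and nonrandomized and sets no success criterion, so false-positive rates matter less than in a confirmatory trial. That also stands. It does not remove the need for one reproducible definition of a named primary endpoint.

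Fourth, the zone can be inferred, because the only definition and the regression agree. That is fair, and the label conflict alone would be minor.

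A reader might infer that the plan loses early failures altogether. It does not: they enter MACE and the Cox model at vessel level. They are absent only from the primary result.

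**Conclusion.** The point holds as a defect in the primary endpoint's definition that should be fixed. As written, the rule can score a failed and repaired lesion as a success, and the endpoint's name does not match its definition or its model.

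The size is unknown. Under an assumed 15% rate, early re-treatment of 20-30% in both groups costs 3.0 to 4.5 percentage points if all re-treated lesions stay open. Shares of 30% and 20% move the odds ratio to 0.86 or 1.16, and less if some lesions narrow again.

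Two stronger readings are not supported. One is that the group comparison is seriously distorted. An assumed split of 50% and 10% would give an odds ratio of 0.52 or 1.93, but nothing in the documents points to such a split, or to which technique would have more early re-treatment. The other is that the significance test is invalid. The modest split moves rejection only from 4.8% to 4.9% or 7.0%, and the trial is not confirmatory. The concern is a biased estimate of the primary result.

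**What to change.** Define the primary event as any of the following:
- in-segment restenosis above 50%, in the zone of METHODS section 2, item 7, at the 13-month film within a stated window;
- angiographically documented in-segment restenosis before that window;
- target lesion revascularization for restenosis before that window.

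Use this one definition in the endpoint name, the group comparison and the logistic model, with stent-only restenosis as a secondary outcome. Report reocclusion separately and state whether it counts in the primary event. Keep stent thrombosis, which item 7 defines by its own criteria, as a separate outcome, so that an acute thrombosis is not scored as restenosis.

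Do not keep early events while dropping event-free patients without a film unless the effect is shown. Report by group the numbers re-treated early, dead and without a film, and give the scheduled-film-only result as a sensitivity analysis. How to handle missing films and deaths in full is a separate matter on which statisticians may differ.

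The cost is rewording plus data work. The date, zone and indication of each early revascularization must be recorded, and existing unscheduled films retrieved across ten centers. Early events are partly symptom-driven, which the film-only analysis helps to show. No extra procedure is needed, and the total of 300 is unchanged.

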be a direct consequence of subintimal stenting. If the cause of the high incidence of restenosis is, in fact, due to use of the subintimal space, newer CTO techniques, which are based on controlled subintimal dissection and reentry methods, also would be expected to be associated with this adverse outcome²⁵⁻²⁸ Now there are only limited data about procedural success of ADR and RDR and retrograde techniques have been demonstrated and the use of subintimal stenting did not adversely impact outcomes^{34, 35}. While prospective studies with longer follow-up are needed to assess the long-term safety and efficacy of sub-intimal stenting.

The purpose of the study was therefore to examine the longer-term outcomes of patient who underwent successful CTO PCI in our program, compare the effect of ADR/RDR on outcomes with everolimus-eluting stents (EES) and assess predictors of long-term events.

METHODS

1. Trial overview and study population.

① This clinical trial is a prospective, exploratory, nonrandomized, multicenter trial evaluating the frequency of angiographic restenosis and clinical outcomes among patients undergoing CTO PCI in intimal stent group using antegrade or retrograde wire escalation (AWE/RWE) techniques and sub-intimal stent group using contemporary antegrade or retrograde dissection and re-entry (ADR or RDR) with everolimus-eluting stents (XIENCE Coronary Stent).

② According to high patient's volume registry studies in CTO lesions, the patients percentage of ADR or RDR strategy application was just only 20-25%³⁶⁻³⁷. If to get 60 patients for ADR or RDR strategies, the minimum CTO number are 300 patients. So in our registry study, 300 CTO cases, to which PCI will be attempted, are prospectively enrolled from December 1 2018 to December 31 2019 in the CTO registries of ten centers. The study was approved by the institutional review board at each site. For patients with multiple treated CTO, only the first CTO attempted was considered for the analysis.

③ Exclusions included age <18-years-old or >85-years-old, left ventricular ejection

fraction $\leq 30\%$, allergy to medications (antiplatelet drugs, heparin, metal alloys, or contrast agents), a planned surgery within 6 months of PCI or planned thrombolysis, pregnant, a life expectancy of <6 months.

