④ Clinical success will be defined as a procedural success without In-hospital MACCEs. In-hospital MACCEs is defined as the composite of non-Q-wave and Q-wave myocardial infarction (MI), recurrent angina requiring urgent repeat revascularization with PCI or coronary bypass surgery, stroke, and death. Non-Q-wave MI is defined as creatine kinase-MB enzyme elevation >3 times the upper limit of normal. When new pathological Q waves, in addition to enzyme elevation, will be observed on the electrocardiogram, the event is defined as a Q-wave MI. In all patients, creatine kinase and creatine kinase-MB is evaluated 6 h after the procedure and until their normalization if levels is abnormal.

⑤ Lesion complexity will be judged using the J-CTO (Multicenter CTO Registry in Japan) score (0 ¼ easy, 1 ¼ intermediate, 2 ¼ difficult, 3 ¼ very difficult) (20) and calculated by allocating 1 point each for: non-tapered proximal cap (ie, blunt or ambiguous), any calcification, any tortuosity, occlusion length >20 mm and any prior unsuccessful attempt. J-CTO score of ≥ 2 was defined as complex.

⑥ CTO proximal cap location is defined according to American Heart Association (AHA) classification and additionally coded as either ostial or non-ostial and proximal (left main, proximal left anterior descending, proximal circumflex or proximal right coronary artery) or distal (all other sites). Cap morphology is coded as blunt or tapered, or as ambiguous when there is lack of clarity over the origin of the ongoing vessel. Calcification within the CTO is coded as none visible, mild (spots only), moderate (<50% of vessel circumference) or severe (>50% of vessel circumference). Tortuosity is assessed at baseline or after subsequent equipment passage and coded as straight (no bend or <45° single bend), slight (>45° single bend), moderate (2 bends >45° or 1 bend >90°) or severe (2 bends >90° or 1 bend >120°).

Disease proximal and distal to the CTO is classified as absent, mild, moderate or severe. Proximal or distal cap side branch is considered present if occurring ≤ 3 mm from the respective CTO cap. Occlusion length is estimated by dual injection, or from apparent length after guidewire crossing. Collaterals are classified according to Cohen and Rentrop and deemed interventional if, on angiographic inspection, are thought amenable to crossing by a guidewire and a microcatheter by the operator.

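### The non-Q-wave MI rule takes no account of CK-MB before PCI, so an elevation already present can be scored as an in-hospital MACCE and a clinical failure

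*Combined protocol and SAP*

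**What the plan says.** All references are to the METHODS part of the combined protocol and SAP.

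- **MI rule (section 2, item 4).** "Non-Q-wave MI is defined as creatine kinase-MB enzyme elevation >3 times the upper limit of normal". The Q-wave branch follows: "When new pathological Q waves, in addition to enzyme elevation, will be observed on the electrocardiogram, the event is defined as a Q-wave MI".
- **Sampling (same item).** In all patients, "creatine kinase and creatine kinase-MB is evaluated 6 h after the procedure and until their normalization if levels is abnormal". No sample before the procedure is scheduled.
- **Where the rule is used (same item).** "In-hospital MACCEs is defined as the composite of non-Q-wave and Q-wave myocardial infarction (MI"), together with urgent repeat revascularization, stroke and death. Then: "Clinical success will be defined as a procedural success without In-hospital MACCEs".
- **Secondary endpoint (section 2, item 1).** In-hospital and 30-day MACE includes acute MI, with no separate definition.
- **Eligibility (section 1, item 3).** The exclusions are age, low ejection fraction, allergy, and "a planned surgery within 6 months of PCI or planned thrombolysis, pregnant, a life expectancy of <6 months". Neither recent MI nor a raised enzyme level is listed. The target occlusion must have TIMI "flow grade 0 and estimated durations of at least 3 months" (section 2, item 2).
- **Data entry (section 1, item 4).** Operators enter the outcome data. No event adjudication is described.

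**The concern.** In-hospital MACCE and clinical success are meant to describe what happened because of, or soon after, the CTO procedure. A fixed cut-off on a post-procedure sample does that only if CK-MB was normal beforehand. The protocol does not ensure this: a patient with a recent infarct in a non-CTO vessel, whose CTO is treated in the same admission, is eligible.

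The two branches of the definition also differ. The Q-wave branch requires the Q waves to be new, whereas the non-Q-wave branch has no requirement of newness. The elevation cannot be read as a rise from the patient's own level, because the multiple is explicitly of the ULN.

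At stake is the in-hospital MI rate and what is built on it. False events would raise the reported complication rate and lower the reported clinical success rate.

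**Working it through.** **1. The plan's own figure.** The only design figure is the enrolment target in section 1, item 2: 60 dissection/re-entry patients at a share of 20% gives 60 / 0.20 = 300, as stated (at 25% it would be 60 / 0.25 = 240). The 300 serves below only as a denominator. The plan gives no expected MI rate and no share of patients with raised enzymes before PCI.

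**2. Scoring example records by the rule as written.**

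| Record | CK-MB before PCI | CK-MB at 6 h | Score | Sound? |
|---|---|---|---|---|
| a | normal | 4 × ULN | MI | yes |
| b | 6 × ULN, falling | 4 × ULN | MI, MACCE, clinical failure | no, nothing new is shown |
| c | normal | 2 × ULN | no MI | yes |

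Record b is the defect. It needs a value still above 3 × ULN at the post-procedure sample; an older MI whose CK-MB has fallen below that level is not scored.

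**3. Does eligibility remove record b?** The exclusion list does not mention it. The 3-month rule dates the target occlusion, not an infarct in another territory. Excluding planned thrombolysis does not remove an MI managed without it.

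**4. Illustrative size.** Let s be the share of patients above 3 × ULN after PCI because of an earlier MI, and t the true procedural MI rate, taken as independent. Both are assumptions.

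Scored rate = s + (1 − s) × t. False events in 300 = 300 × s × (1 − t).

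| s | Scored rate, t = 3% | False events | Scored rate, t = 6% | False events |
|---|---|---|---|---|
| 0 | 3.00% | 0 | 6.00% | 0 |
| 1% | 0.01 + 0.99 × 0.03 = 3.97% | 2.9 | 0.01 + 0.99 × 0.06 = 6.94% | 2.8 |
| 3% | 0.03 + 0.97 × 0.03 = 5.91% | 8.7 | 0.03 + 0.97 × 0.06 = 8.82% | 8.5 |
| 5% | 0.05 + 0.95 × 0.03 = 7.85% | 14.6 | 0.05 + 0.95 × 0.06 = 10.70% | 14.1 |

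**5. Weight of one event.** With the planned 60 dissection/re-entry patients and 300 − 60 = 240 others, one false event moves the group rate by 1/60 = 1.7 or 1/240 = 0.4 percentage points. This shows how sensitive small groups are to a single event. It is not evidence of bias.

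**The case against.** The strongest reply is that the gap is narrow and falls on lesser outcomes. Much of it stands.

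- **Few patients may be affected.** Intravenous hydration on the days before PCI (section 3, item 1) points to scheduled procedures, and nothing suggests that CTO PCI soon after an MI is common. The size is wholly assumed.
- **Clinical success is defined but not a listed endpoint.** Section 2, item 1 names technique and procedure success, and procedural success (item 3) is purely angiographic. The link to the MACE secondary endpoint is an inference: its components are worded differently from MACCE, and the MI rule is carried over only because no other is given.
- **The primary endpoint is untouched, and the study is called exploratory.**

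A reader might infer two stronger things. One is that every MI a patient arrives with will be counted; that fails, because CK-MB must still exceed 3 × ULN after PCI. The other is that the technique comparison is biased because acute presenters are steered to simpler wire techniques. The documents show no such route. Section 3, item 5 puts wire escalation first in all patients, bases strategy on four angiographic characteristics, and leaves the choice to the operator after failure. Section 2, items 8 and 9 also choose by anatomy or by failure of the first approach. Presentation appears in none of these.

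None of this removes record b. The written rule gives a wrong score there, and no adjudication step is described that would correct it.

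**Conclusion.** The point holds in a limited form. As written, the non-Q-wave MI rule can count an elevation that predates the procedure as an in-hospital MACCE and a clinical failure. It can also do so in the in-hospital and 30-day MACE secondary endpoint, provided that endpoint uses the same MI definition.

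The documents do not allow the size to be determined. Under the assumed ranges it is roughly 3 to 15 false events in 300; if no enrolled patient has a raised CK-MB before PCI, it is zero. The 13-month restenosis endpoint is not affected, and no bias between techniques is shown. The case for correcting the rule rests on the wrong result it gives in a permitted patient and on the low cost of the change, not on a demonstrated distortion.

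**What to change.** In section 2, item 4, add a baseline clause and record the last clinical CK-MB before PCI where one exists:

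1. **Last value normal, or none on file and no recent MI:** keep the present rule, above 3 × ULN. The default is needed because no pre-procedure draw is scheduled; without it, a patient with no earlier value and 10 × ULN afterwards could not be classified.
2. **Last value raised:** count a non-Q-wave MI only if the post-procedure value exceeds both 3 × ULN and the last pre-procedure value.
3. **Recent MI and no pre-procedure value:** count only a new Q-wave MI or a clinically diagnosed new MI.
4. **Reporting:** list the raised-baseline and recent-MI patients separately, and give the in-hospital MI rate with and without them.

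The text should also state the time window for a recent MI, what counts as clinically diagnosed, and whether the MACE secondary endpoint uses this definition.

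**Cost.** A short addition to the definition, one database field for the last CK-MB plus a flag for recent MI, and one extra reported rate. No added sampling, visits or patients. The reported MI rate may fall slightly. A few patients may still be misclassified: a procedural MI on top of a falling baseline can be missed, and an admission MI still evolving at PCI (2 × ULN before, 5 × ULN after) would still be counted. The separate listing lets a reader see how much depends on them.
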